11.2.1 Adverse Events of Special Interest (AESI)

The number and percentage of subjects having AESI will be tabulated by MedDRA system organ class and preferred term. Specific AESI will be identified by the following search criteria in [Table 7](#).

Table 7. Adverse Events of Special Interest

Adverse Event of Special Interest	Search Criteria	Event Definition/ Medical Concept
Microcystic Keratopathy	CMQ "80000152"; Preferred Terms: Acquired corneal dystrophy, Ciliary hyperaemia, Corneal abrasion, Corneal cyst, Corneal decompensation, Corneal defect, Corneal degeneration, Corneal deposits, Corneal disorder, Corneal dystrophy, Corneal epithelial microcysts, Corneal epithelium defect, Corneal erosion, Corneal irritation, Corneal lesion, Corneal oedema, Corneal opacity, Deposit eye, Dry eye, Eye pain, Foreign body sensation in eyes, Keratitis, Keratopathy, Lacrimation increased, Limbal swelling, Ocular toxicity, Photophobia, Slit-lamp tests abnormal, Topography corneal abnormal, Vision blurred	Any adverse event report identified by search criterion

11.2.1.1 Adverse Event of Special Interest

The number and percentage of subjects experiencing at least one AESI for each of the following events will be summarized:

- Any AESI
- Any AESI by NCI CTCAE grade
- Any AESI with NCI CTCAE grade 3 or 4
- Any serious AESI
- Any AESI leading to discontinuation of ABT-414
- Any AESI leading to dose interruption of ABT-414
- Any AESI leading to dose reduction of ABT-414

11.2.1.2 Time to Onset of Adverse Event of Special Interest

For specified AESIs, time to the first occurrence (onset) the event will be assessed using survival analysis methodology (Kaplan-Meier estimates) separately for all AESIs, for all AESIs with NCI CTCAE grade ≥ 2 , and for all AESIs with NCI CTCAE grade ≥ 3 .

Time to onset will be measured in days relative to the day of a subject's first dose of study drug (ABT-414/TMZ/lomustine) to the start date of the first occurrence of AESI. If a subject has not experienced an AESI, the subject will be censored on the day of the subject's last assessment (i.e., the day of the subject's last known laboratory assessment, last known vital sign assessment, last known physical exam, last known ocular exam, last known tumor assessment, or last known follow-up visit, whichever is the latest) or 35 days from the subject's last ABT-414 treatment, whichever is earliest; if the subject has not experienced an AESI and had no post-baseline assessment (i.e., none of laboratory assessment, vital sign assessment, physical exam, ocular exam, or tumor assessment), the subject will be censored on the day of the subject's first study drug (ABT-414/TMZ/lomustine).

Median onset time will be estimated using a Kaplan-Meier method with corresponding 95% CI for the median for each treatment arm.

11.3 Deaths

The number and percentage of subject deaths will be summarized 1) for deaths occurring while the subject was still receiving study drug (ABT-414/TMZ/lomustine) in this study; 2) for deaths occurring off-treatment within 35 days after the last dose of study drug (ABT-414/TMZ/lomustine); and 3) for all deaths in this study regardless of the number of days after the last dose of study drug (ABT-414/TMZ/lomustine).

Similarly, the number and percentage of subject deaths will be summarized for deaths occurring while the subject was still receiving 1) ABT-414; 2) within 35 days after the last dose of ABT-414; and 3) for all deaths regardless of the number of days after the last dose of ABT-414.

11.4 Analysis of Laboratory, Vital Signs, and ECG Data

Biochemical parameters (serum creatinine, total bilirubin, AST, ALT, alkaline phosphatase, phosphate, total protein, albumin, sodium, potassium, calcium, and chloride) will be collected at baseline (all Arms), and Day 1 of each cycle (all Arms).

Hematological parameters (WBC, absolute neutrophil count, lymphocytes, hematocrit, hemoglobin, and platelet count) will be collected at baseline (all Arms), Day 1 of each cycle (all Arms), Day 14 of each cycle (Arms 1 and 2 only), Day 21 of each cycle (Arms 1 and 3B only), and Day 28 of each cycle (Arm 3A only).

Vital sign parameters (diastolic/systolic blood pressure, pulse rate, and body temperature (°C)) will be collected at baseline (all Arms), Day 1 of each cycle (all Arms), Day 14 of each cycle (Arms 1 and 2 only), and Day 28 of each cycle (Arm 3A only), and follow-up visit if clinically indicated/relevant.

Twelve-lead ECG data will be collected at baseline, immediately after ABT-414 dosing on Day 1 of Cycle 1 and Cycle 3 (Arms 1 or 2 only).

For hematological, biochemical, and vital sign parameters, changes from baseline are analyzed for each post-baseline visit (as specified in Section 6.0 Analysis of Conventions) and the final visit. If more than one measurement exists for a subject on a particular day, an arithmetic average will be calculated. The average will be considered to be the subject's measurement of that day. Descriptive statistics will be presented for baseline, each post-baseline, and the final visit by each treatment arm. Mean change from baseline to each post-baseline visit and the final visit within each treatment arm will also be presented. The highest and lowest values of each hematological parameter will be identified for each subject, and descriptive statistics for mean change from baseline within each treatment arm will be presented.

Biochemistry and hematology determinations will be categorized according to NCI CTCAE version 4.0 grades, and shifts from baseline grades to maximum and final post-baseline grades will be assessed. The baseline and final grades will be defined respectively as the grade of the last measurement collected prior to or on randomization, or if missing, then prior to or on the first dose of study drug (ABT-414/TMZ/lomustine), and as the grade of the last post-baseline measurement collected no more than 35 days after the last dose of study drug (ABT-414/TMZ/lomustine). If multiple values are available for a post-baseline measurement, then the value with the highest NCI CTCAE

grade will be used in the assessment of shift. Frequency and percentage of subjects will be presented by treatment arm: 1) baseline grade vs. maximum post-baseline grades, and 2) baseline grade vs. final post-baseline grade. Frequency and percentage of subjects experiencing a shift from baseline grades of 0 to 2 to maximum post-baseline grades of 3 to 4, and from baseline grades of 0 to 2 to final post-baseline grades of 3 to 4 will be presented by treatment arm.

Detailed listings of data for subjects experiencing NCI CTCAE grade 3 to 4 biochemistry and hematology values will be provided. All measurements collected, regardless of the number of days after the last dose of study drug, will be included in these listings.

Descriptive summary statistics for categorical ECG data will be presented for baseline and Day 1 of Cycle 1 and Cycle 3 (Arms 1 or 2 only). Visit window in [Table 2](#) will not be applied to the ECG data. Shift tables will also be provided.

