6.3.4 Day 21 of each cycle - Arm 1 and 3B patients only

All day 21 evaluations should be performed within 3 days before or 3 days after day 21 of the cycle.

- Hematology (as 6.2 - this can be omitted once treatment at the present dose level was shown to cause only grade 1 or less hematological toxicity at day 21 and only grade 2 or less at day 28).

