4.2 Design Diagram

This is a comparative randomized, open label, multicenter, multi-arm, Phase II study. The study will consist of three treatment arms; Arm 1 (ABT-414 plus TMZ), Arm 2 (ABT-414 monotherapy), and Arm 3 (mixed control arm of lomustine or TMZ). Subjects will be randomized in a 1:1:1 ratio at the EORTC headquarters after verification of the eligibility criteria discussed in Section 3 of the study protocol.

Arm 1: Subjects will be treated with ABT-414 1.0 mg/kg IV infusion over 30 to 40 minutes once every 2 weeks in combination with TMZ 150 mg/m² Day 1 to 5, for the first 28-day cycle, with dose escalation to 200 mg/m² in subsequent cycles in case of adequate tolerance and until one of the treatment withdrawal criteria has been met. In this Arm 1 the schedule of clinical and lab assessments follows the cycle of TMZ (a delay of TMZ delays the assessment schedule, withholding ABT-414 does not affect the assessment schedule).

Arm 2: Subjects will be treated with ABT-414 monotherapy 1.0 mg/kg IV infusion over 30 to 40 minutes once every 2 weeks until one of the treatment withdrawal criteria has been met.

Subjects in the control arm (Arm 3) will be treated according to the timing of relapse.

Arm 3A: Subjects relapsing during TMZ treatment or within the first 16 weeks after the first day of the last TMZ cycle will be treated with lomustine 110 mg/m² on Day 1 of every 42-day treatment period. Treatment will continue until one of the treatment withdrawal criteria has been met. Lomustine will be given for a maximum of 1 year.

Arm 3B: Subjects relapsing 16 weeks or more after the first day of the last TMZ cycle will be treated with TMZ 150 mg/m² on Day 1 to 5 for the first 28-day cycle, with dose escalation to 200 mg/m² in subsequent cycles in case of adequate tolerance. Treatment will continue until one of the treatment withdrawal criteria has been met.

Treatment should start within 96 hours from randomization. Treatment will be administered until one of the withdrawal criteria described in Section 5.4 of the study protocol has been met. Treatment at further progression will be according to investigators discretion.

Day 1 of the first cycle will be the first day when the study medication is taken.

A schematic of the study design is shown in [Figure 1](#). The study procedures for each visit are outlined in [Table 1](#).

Figure 1. Study Schematic

[figure not shown]

Table 1. Study Activities

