During the treatment period, all time points and corresponding time windows are based on Study Rx Days, unless specified otherwise. For longitudinal analyses, especially for the laboratory data, the time windows in Table 2 describe how data collected at protocol specified visits will be assigned. If more than one observation is included in a time window, the observation closest to the nominal day should be used. If there are two observations equally distant to the nominal day, the later one will be used in analyses.

Table 2. Visit Window

Study Visit (Week)*	Nominal Study Rx Day	Time Window (Study Rx Days Range)
Baseline	-	By baseline definition
2	15	2 to ≤ 18
3	22	19 to ≤ 25
4	29	26 to ≤ 32
...
X	$7 \cdot X + 1$	$7 \cdot X - 2$ to $\leq 7 \cdot X + 4$

* ECG at baseline and only Day 1 of Cycle 1 and 3, immediately after ABT-414 infusion and only subjects treated with ABT-414 (Arms 1 or 2).

Time-to-Event Endpoints

All time to event (TTE) endpoints are defined using a time variable and an event indicator. The time variable represents the time from a pre-defined time origin to the onset of a predefined event of interest or the last time when adequate assessments have been made to rule out the onset of the event. The latter case indicates that the endpoint has been right-censored. The event indicator is set to 1 if the event has been observed during the course of the study and 0 if it is censored. When multiple assessments are needed to ascertain the occurrence of an event, the earliest date among all of these assessments is taken to be date of the event or censoring. The time variable will be computed in days and converted into months (1 month = 30.4375 days) for analysis of TTE endpoints. When no post-randomization observations are available for a subject for any given endpoint, then the endpoint is taken to be censored on the date of randomization.

All TTE endpoints defined in this study are concerned with only the first incidence of an event of interest, and recurrence of the same event is not considered. An event, however, may be defined in a composite fashion, i.e., as the occurrence of one among several different outcomes. An example of such an endpoint is PFS where the event is either disease progression or death. The composite event is observed when at least one of the component events occurs, and the time to the earliest among the occurring component events is considered to be the TTE for the composite event.

Prior and Concomitant Medications

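### Weekly laboratory means for the pooled control arm (SAP 11.4) partly show which control drug had blood scheduled that week, and later day-21 means may over-represent patients with toxicity

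*SAP*

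**What the plan says.** SAP 11.4 states that for hematology, biochemistry and vital signs "changes from baseline are analyzed for each post-baseline visit (as specified in Section 6.0 Analysis of Conventions) and the final visit". It adds "Descriptive statistics will be presented for baseline, each post-baseline, and the final visit by each treatment arm" and "Mean change from baseline to each post-baseline visit and the final visit within each treatment arm will also be presented". The reference to SAP 6.0 leads to Table 2: "For longitudinal analyses, especially for the laboratory data, the time windows in Table 2 describe how data collected at protocol specified visits will be assigned". Those windows are calendar weeks counted from the first dose, whatever the cycle length.

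SAP 4.2 lists the control group as a single arm: "Arm 3 (mixed control arm of lomustine or TMZ". Lomustine (3A) is given in 42-day periods and TMZ (3B) in 28-day cycles. The SAP plans no 3A/3B split of laboratory results.

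SAP 11.4 also shows that draw days depend on the drug. Hematology is taken on day 1 in all arms and day 14 in Arms 1 and 2, then "Day 21 of each cycle (Arms 1 and 3B only), and Day 28 of each cycle (Arm 3A only". Biochemistry is taken on day 1 of each cycle in all arms. On the day-21 count, Protocol 6.3.4 says "this can be omitted once treatment at the present dose level was shown to cause only grade 1 or less hematological toxicity at day 21", with the further condition of grade 2 or less at day 28. SAP Table 1, footnote 7, repeats the rule.

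**The concern.** A table of mean change by week is read as a time course. That reading needs roughly the same patients, at a comparable point in their cycle, in each column. In Arm 3 neither holds: the contributing drug changes between weeks, and in some shared weeks the two drugs are at opposite points of their cycles. Arm 3 is the comparator for both ABT-414 arms, so readers will set its column beside theirs.

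A second, separate effect concerns Arms 1 and 3B. If patients with mild counts skip later day-21 tests and patients with worse counts do not, the day-21 mean can fall over time with no change in the underlying effect.

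**Working it through.** **Inputs.** Table 2 windows (SAP 6.0); cycle lengths of 42 and 28 days (SAP 4.2); draw days (SAP 11.4); lomustine nadir at days 28 to 35 (Protocol 5.5.2.1.1); TMZ nadir at about day 21 with recovery checked on day 28 or 29 (Protocol 5.5.3). Treatment is taken as on schedule.

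**Windows.** Week X covers days 7X − 2 to 7X + 4. Week 3 gives 19 to 25 and week 4 gives 26 to 32, as Table 2 states.

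**Scheduled hematology days after the first dose, cycle c.**
- 3A: 42(c − 1) + {1, 28} = 28, 43, 70, 85, 112, 127, 154, 169, which fall in weeks 4, 6, 10, 12, 16, 18, 22, 24.
- 3B: 28(c − 1) + {1, 21} = 21, 29, 49, 57, 77, 85, 105, 113, 133, 141, 161, 169, which fall in weeks 3, 4, 7, 8, 11, 12, 15, 16, 19, 20, 23, 24.

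| Arm 3 hematology to week 24 | Weeks | Count |
|---|---|---|
| TMZ only | 3, 7, 8, 11, 15, 19, 20, 23 | 8 |
| Lomustine only | 6, 10, 18, 22 | 4 |
| Both | 4, 12, 16, 24 | 4 |

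So (8 + 4)/16 = 75% of populated weeks hold one drug. In weeks 4 and 16, lomustine contributes day 28 of its cycle (study days 28 and 112) and TMZ contributes day 1 (study days 29 and 113). Only weeks 12 and 24 are day 1 for both.

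**Biochemistry (day 1 only).** 3A falls in weeks 6, 12, 18, 24 and 3B in weeks 4, 8, 12, 16, 20, 24. That is 8 populated weeks, of which 6 hold one drug.

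**Illustration of the effect.** Assume constant platelet changes of −100 on lomustine and −40 on TMZ (×10⁹/L; my assumption, not in the documents). Take the 60:40 historical split in Protocol 1.2. A shared week then reads 0.6 × (−100) + 0.4 × (−40) = −76.

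| Week | 3 | 4 | 6 | 7 | 8 | 10 | 11 | 12 |
|---|---|---|---|---|---|---|---|---|
| Arm 3 mean | −40 | −76 | −100 | −40 | −40 | −100 | −40 | −76 |

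Neither drug changes over time, yet the arm mean does. For splits from 50:50 to 70:30 the shared weeks range from −70 to −82; the single-drug weeks do not move.

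**Day-21 omission.** Study day 49 (week 7) is cycle 2, day 21. Protocol 5.5.3 lets patients with no or only grade 1 toxicity in cycle 1 escalate. Escalation is a new dose level, so their day-21 test is due again in week 7. Patients with a grade 3 or 4 nadir are reduced, also to a new level, and patients with grade 2 at day 21 do not qualify to omit. Omission at week 7 is therefore open mainly to low-toxicity patients who did not escalate. It can become general only from about week 11 (cycle 3, study day 77).

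**Other arms.** Arm 2 is drawn on days 1 and 14 of each 28-day cycle, with no scheduled change of drug or patients. Arm 1 keeps one regimen, so only the day-21 effect applies to it.

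**The case against.** The strongest reply is that these tables are descriptive and the important toxicity outputs lie elsewhere. SAP 11.1 rules out comparisons, p-values and confidence intervals for safety. Highest and lowest values per patient, CTCAE shifts, grade 3 to 4 listings, potentially clinically significant values and the hepatotoxicity criteria do not use the weekly windows. SAP 6.0 also reports N with every continuous summary, so swings in the number contributing would be visible. All of this stands, and it keeps the point minor. It does not make the weekly table right: N does not say which drug the patients took.

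The pattern is also cleaner on paper than it will be in the data. Dose delays shift later cycles, and the ±3-day tolerances in Protocol 6.3.4 and 6.3.5 can move a value by a window: TMZ day 18 falls in week 2 and lomustine day 25 in week 3. This blurs the switching without removing its cause.

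A reader might infer that the day-21 test stops for patients without toxicity, so that means from week 7 onward come only from patients who had toxicity. The documents do not support that. Omission is permitted, not required; the condition is low-grade toxicity, not none; it applies per dose level; and it covers all hematological toxicity, so a calculation on platelets alone would not size it.

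**Conclusion.** The Arm 3 point holds on the documents' own schedule and windows: 12 of 16 hematology weeks and 6 of 8 biochemistry weeks to week 24 contain a single control drug, and two of the four shared hematology weeks mix different cycle phases. The counts assume on-schedule treatment. The Arm 3 weekly trend is therefore partly an artefact of scheduling.

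The day-21 point holds in direction only. In Arms 1 and 3B, means from about week 11 can over-represent patients with toxicity; the documents give no basis for a size.

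A reader might conclude that toxicity information is lost, or that laboratory results in every arm are distorted. Neither follows: Arm 2 is unaffected, the change of drug is confined to Arm 3, and the main toxicity outputs are free of the weekly windows. Severity is minor.

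**What to change.** In SAP 11.4:
- Present visit-level laboratory means for Arms 3A and 3B in separate columns, by cycle and cycle day: pre-dose day 1, TMZ day 21 and lomustine day 28.
- For day-21 means after the first cycle at a dose level, show the number tested and the number allowed to omit the test. Splitting 3A from 3B does not cure this selection.

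There is precedent: SAP 11.4 already exempts ECG data from the Table 2 windows.

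Do not restrict cross-arm displays to weeks 12 and 24, although both control drugs are pre-dose then. That would discard all early data and favour patients still on treatment. With the assumed control median PFS of 2.6 months and an exponential curve (my assumption), week 12 is 84/30.4375 = 2.76 months and 0.5^(2.76/2.6) ≈ 48% remain progression-free; at week 24 (5.52 months) about 23% do.

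The cost is SAP wording and table shells, with no new data and no effect on efficacy analyses. The tables gain a few columns with smaller numbers in each: about 48 and 32 at the start if Arm 3 has 240/3 = 80 patients split 60:40.

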11.4.1 Assessment of Potentially Clinically Significant Laboratory Values

For selected laboratory variables, the number and percentage of subjects who had at least one post-baseline observation meeting the pre-defined criteria for potentially clinically significant values will be provided for each variable. If a subject did not have the laboratory measurement at baseline but had a post-baseline measurement which met the pre-defined criteria, this subject is considered as meeting the criteria for potentially clinically significant laboratory values for the measurement.

Pre-defined criteria for potentially clinically significant laboratory values are given in [Table 8](#) and [Table 9](#) below based on NCI CTCAE criteria:

Table 8. Criteria for Potentially Clinically Significant Laboratory Values – Hematology Variables

Hematology Variables	Units	Definition of Potentially Clinically Significant Values (NCI CTCAE Grade ≥ 3)
Hemoglobin	g/L	< 80
White blood cell count	$10^9/L$	< 2
Neutrophil count	$10^9/L$	< 1
Lymphocyte count	$10^9/L$	< 0.5
Platelet count	$10^9/L$	< 50

Table 9. Criteria for Potentially Clinically Significant Laboratory Values – Chemistry Variables

Chemistry Variables	Units	Definition of Potentially Clinically Significant Values (NCI CTCAE Grade ≥ 3)	
		Low	High
Total bilirubin			> $3.0 \times \text{ULN}$
Albumin	g/L	< 20	
Aspartate aminotransferase (AST/SGOT)			> $5.0 \times \text{ULN}$
Alanine aminotransferase (ALT/SGPT)			> $5.0 \times \text{ULN}$
Alkaline phosphatase			> $5.0 \times \text{ULN}$
Creatinine			> $3.0 \times \text{ULN}$
Sodium	mmol/L	< 130	> 155
Potassium	mmol/L	< 3.0	> 6.0
Total calcium	mmol/L	< 1.75	> 3.1

11.4.2 Assessment of Hepatotoxicity

The number and percentage of subjects with maximum treatment-emergent laboratory values meeting the following criteria were summarized to assess potential hepatotoxicity.

Potential hepatotoxicity criteria defined in Hy's law:

- $\text{ALT} \geq 3 \times \text{ULN}$ and $\text{total bilirubin} \geq 2 \times \text{ULN}$

- $AST \geq 3 \times ULN$ and total bilirubin $\geq 2 \times ULN$
- ALT and $AST \geq 3 \times ULN$ and total bilirubin $\geq 2 \times ULN$

The maximum ratio relative to the ULN will be used to determine if subjects met the criteria listed above. The ALT, AST, and total bilirubin values do not need to be concurrent in order to meet the defined criteria as long as collected up to 35 days following the last dose date of study drug (ABT-414/TMZ/lomustine). For ALT, AST, and total bilirubin, a subject will be counted if the post-baseline laboratory value up to 35 days following the last dose date of study drug (ABT-414/TMZ/lomustine) met the above criteria regardless of the baseline laboratory value (i.e., the post-baseline laboratory value does not need to be worse than the baseline laboratory value).

A listing of all ALT, AST, total bilirubin, and alkaline phosphatase values will be provided for all subjects who meet any of the criteria defined above.

11.5 Analysis of Vital Signs Using Criteria for Potentially Clinically Significant Vital Sign Values

Vital signs values will be assessed for potential clinical significance through the application of criteria developed by the sponsor as detailed in [Table 10](#).

Table 10. Criteria for Potentially Clinically Significant Vital Sign Values

Vital Signs Variables	Criterion	Definition of Potentially Clinically Significant Values
Systolic blood pressure	High	Value ≥ 160 mmHg
Diastolic blood pressure	High	Value ≥ 100 mmHg
Heart rate	Low	Value ≤ 50 bpm
	High	Value ≥ 120 bpm
Temperature	Low	Value $\leq 32^\circ\text{C}$
	High	Value $> 40^\circ\text{C}$

The number and percentage of subjects with post baseline values meeting Criteria for Potentially Clinically Significant Vital Signs values will be summarized. The baseline will be defined as the last non-missing measurement collected prior to or on the first dose

of study drug (ABT-414/TMZ/lomustine). A separate listing will be provided that presents all of the subjects and values that meeting the criteria. No comparisons of the rates of subjects met the above criteria between the treatment arms will be performed.

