6.4 After end of treatment

Every 12 weeks (+/- 14 days) since last protocol treatment administration until death or loss to follow up:

- Survival follow up
- Further anti-cancer treatments/modalities
- Physical examination including WHO performance status and neurological examination
- Ocular examination if clinically indicated
- Vital signs if clinically relevant
- Steroid intake
- Concomitant medication collection if clinically relevant
- Assessment of all adverse events according to CTCAE 4.0 (i.e. for events not resolved after the end of treatment and new events related to study treatment)

If a subject is unable to return to the clinic for this visit, survival follow up and other assessments as appropriate may be completed via phone.

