6.0 Analysis Conventions

This section provides general considerations for data handling, summary, and analysis. This also includes general definitions of certain kinds of endpoints. More details about specific endpoints and additional analysis methods, as needed, will be specified within the description of analysis of data in this SAP.

Continuous variables will be summarized by sample size (N), mean, standard deviation (St. Dev.), median, minimum, and maximum. Frequency and percentage will be provided for categorical variables and 95% confidence intervals (CIs) will be generated for parameter estimates of interest.

Dealing with Multiple Values on the Same Day for Lab and Vital Signs Parameters

In cases where multiple values for the same variable are collected on the same day (including baseline visit and post-baseline visits), the arithmetic average will be calculated and used as the value for that day for mean changes in laboratory and vital signs parameters.

Definition of Baseline Observation

Unless otherwise specified, the baseline observation is defined as the last non-missing measurement collected prior to or on randomization. If no measurement collected prior to or on randomization, then the last non-missing observation prior to or on the first dose date of study drug (ABT-414/TMZ/lomustine) is considered.

Definition of Final Observation

For lab and vital sign parameters, the final observation is defined as the last non-missing post-baseline measurement collected during the study.

Definition of Study Rx Days (Days Relative to the First Dose of Study Drug)

Study Rx Days are calculated for each time point relative to the first dose date of study drug (ABT-414/TMZ/lomustine). They are defined as the number of days between the day of the first dose of study drug (ABT-414/TMZ/lomustine) and the specific time point. Rx days are negative values when the time point of interest is prior to the first study drug dose day. Rx days are positive values when the time point of interest is after the first study drug dose day. The day of the first dose of study drug (ABT-414/TMZ/lomustine) is defined as Study Rx Day 1, while the day prior to the first study drug dose is defined as Study Rx Day -1 (there is no Study Rx Day 0).

Definition of Analysis Windows

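### As worded, the SAP's abnormal-vital-sign and abnormal-laboratory summaries have no end date, so vital signs taken selectively long after the last dose would count under the study treatment.

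*SAP*

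**What the plan says.** **Summaries with no end date**
- SAP 11.5, vital signs: "The number and percentage of subjects with post baseline values meeting Criteria for Potentially Clinically Significant Vital Signs values will be summarized".
- SAP 11.4.1, laboratory values: it counts "subjects who had at least one post-baseline observation meeting the pre-defined criteria".
- SAP 11.4: the maximum post-baseline CTCAE grade and each subject's highest and lowest hematology values carry no limit.
- SAP 6.0, laboratory and vital signs: "the final observation is defined as the last non-missing post-baseline measurement collected during the study". This feeds the final-visit mean change in 11.4.

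**Neighbouring analyses with an end date**
- SAP 11.4 defines the final shift grade "as the grade of the last post-baseline measurement collected no more than 35 days after the last dose of study drug".
- SAP 11.4.2 (hepatotoxicity) and SAP 11.1 (treatment-emergent adverse events) also stop 35 days after the last dose.

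**The protocol**
- Section 8.2.3.7 restricts safety analyses to forms up to the last safety assessment before progression or further anti-tumoral therapy. The same paragraph says the analyses cover the whole study duration and refers to severe grades emerging in follow-up.
- Section 6.4 schedules visits every 12 weeks (plus or minus 14 days) after the last administration until death or loss to follow-up, and includes "Vital signs if clinically relevant". SAP 11.4 repeats this for vital signs: "and follow-up visit if clinically indicated/relevant".
- Section 7.2.1.8 collects adverse events for 49 days after study drug stops.

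**The concern.** The drafters wrote a 35-day limit where they wanted one. A programmer who follows 11.4.1 and 11.5 literally would therefore apply none. Within 11.4 itself, the final grade is capped and the maximum grade beside it is not.

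Post-treatment vital signs can exist, and they are collected selectively: a reading taken only when clinically relevant is plausibly more likely to be abnormal than a scheduled one. Treatment after progression is at the investigator's discretion (SAP 4.2), and protocol 1.2 describes bevacizumab as widely used in recurrent disease. Hypertension, tachycardia or fever during next-line therapy or the terminal phase could then appear in a table read as the safety profile of ABT-414, TMZ or lomustine.

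The exposure to this is also unequal. The longer subjects live after stopping treatment, the more follow-up visits they have. Under the trial's own hypothesis that favours a higher count in the ABT-414 arms, for a reason unrelated to drug toxicity.

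**Working it through.** The plan states no figure on this point, so the check is of text and dates, with one illustration.

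**1. Windows side by side**

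| Summary | SAP section | Last day counted |
|---|---|---|
| Treatment-emergent AEs | 11.1 | last dose + 35 days |
| Final shift grade | 11.4 | last dose + 35 days |
| Hepatotoxicity | 11.4.2 | last dose + 35 days |
| Maximum shift grade | 11.4 | none stated |
| Highest/lowest hematology | 11.4 | none stated |
| Final observation, mean change | 6.0, 11.4 | none (during the study) |
| Abnormal laboratory table | 11.4.1 | none stated |
| Abnormal vital-sign table | 11.5 | none stated |

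**2. When follow-up vital signs fall**
- First visit: 84 − 14 = day 70 to 84 + 14 = day 98 after the last dose.
- The earliest is 70 − 35 = 35 days past the SAP limit and 70 − 49 = 21 days past the protocol's AE collection period.
- Every 12-weekly follow-up vital sign is therefore outside both windows.

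**3. Laboratory values**
- SAP 11.4 schedules biochemistry and hematology only at baseline and during cycles. Protocol 6.4 lists no laboratory tests.
- Late values arise only unscheduled, for example hepatic follow-up to resolution under protocol Appendix L.

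**4. Unequal follow-up, illustration only**
- Inputs from SAP 4.4: median PFS 2.6 v 4.8 months and median OS 7 v 12.9 months (control v ABT-414).
- Rough version, using the difference of medians as survival after progression and 30.4375 days per month:
  - Control: (7.0 − 2.6) × 30.4375 = 134 days; 134/84 = 1.6, so one full 12-week interval.
  - ABT-414: (12.9 − 4.8) × 30.4375 = 247 days; 247/84 = 2.9, so two full intervals.
- Simulation, 400,000 subjects per arm. Assumptions: exponential PFS, exponential post-progression survival calibrated to the OS medians, treatment until progression, data cut-off uniform between 13 and 31 months after randomization (13 months of follow-up after an 18-month accrual, protocol 8.1.1), and a visit every 84 days after treatment stops.
  - Mean follow-up visits per subject: about 1.9 (ABT-414) v 1.1 (control).
  - At least one follow-up visit: 66% v 54%.

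**5. What cannot be computed**
- The documents do not say how often vital signs would be taken at these visits, or how often a reading would meet a Table 10 threshold. The number of affected values is therefore unknown.

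**The case against.** **The protocol may already exclude these values.** The SAP says it elaborates methods for data as outlined in the protocol, and it does not withdraw the cut-off in 8.2.3.7. On that reading, values after progression or on next-line therapy are out. This stands in part. A reader might infer that the documents establish that next-line values are counted, and they do not. But 8.2.3.7 also says whole study duration, the SAP does not repeat its cut-off, and the SAP's own limits run from the last dose rather than from progression. The tables as worded either depart from the protocol or are unbounded.

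**Randomised arm.** A reader might infer that late values are charged to the randomised arm. SAP 5.0 classifies the safety population by treatment received. EORTC, which uses the assigned arm for subjects who started that treatment, does not produce the 11.5 table (SAP 12.0).

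**Laboratory values.** A reader might give the laboratory half equal weight. Nothing is scheduled in follow-up, and the SAP 11.4 remark about including measurements regardless of days since last dose concerns listings only.

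**Percentages.** It is tempting to convert visits into flagged subjects. Assuming 2%, 5% or 10% of visits give a Table 10 value yields 3.6%, 8.7% or 16.2% on ABT-414 against 2.2%, 5.4% or 10.3% on control; at 0.5% it is 0.9% v 0.6%. No such rate is in the documents, the thresholds are high, vital signs at these visits are optional, and other assessments may be done by phone. The gap also needs the full assumed benefit on PFS and OS. With equal PFS and OS it vanishes.

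**Unequal observation on treatment is larger.** In the same simulation, mean time to treatment stop is about 199 v 113 days. With readings every 14 days in Arms 1 and 2, that is 199/14 ≈ 14. In control it is 113/28 ≈ 4 (Arm 3B, Day 1 of 28-day cycles) to 113/21 ≈ 5 (Arm 3A, two readings per 42 days). A date cut-off leaves this untouched. That is correct, but those readings are scheduled and taken on study drug. The late ones are neither.

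**Two definitions of final.** Both are explicit, so a programmer is not left guessing. The mean-change and grade tables would still use different windows under the same label.

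**Conclusion.** The point holds as a defect in the SAP's safety data windows. Five summaries have no end date while three neighbouring ones stop at 35 days, and the open-ended ones do not follow the cut-off in protocol 8.2.3.7. The practical route of contamination is follow-up vital signs, collected selectively from about day 70 onward. The laboratory contribution is sporadic.

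The only size that can be given is the visit imbalance of about 1.9 v 1.1 per subject. It rests on the design medians, exponential times, treatment until progression and a cut-off at 13 to 31 months. It is not an estimate of falsely flagged subjects, and it does not show that ABT-414 would appear less safe in practice.

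The consequence is limited. SAP 11.1 provides no safety p-values or confidence intervals, and SAP 11.5 makes no between-arm comparison of vital-sign rates. No efficacy result or error rate is affected. The by-arm percentages will nevertheless be read side by side, and the correction is cheap, so it should be made.

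**What to change.** - In SAP 6.0 (final observation), 11.4 (maximum grade, highest/lowest hematology values, final visit), 11.4.1 and 11.5, count only values after the first dose and up to 35 days after the last dose, the limit already used for the final shift grade and in 11.4.2. Exclude values after the start of new anti-cancer therapy.
- State how this rule relates to protocol 8.2.3.7, including its progression cut-off and its whole-study wording, and to the 49-day AE collection period in protocol 7.2.1.8. If the adverse-event window is changed, change this one with it.
- Keep later values in listings, as 11.4 already does for grade 3 to 4 laboratory values.

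The cost is a short SAP wording change and one date filter in the programs. The small downside is that late abnormalities would appear only in listings. The filter does not address the different frequency of scheduled readings on treatment.
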